5.9. Electrocardiography

ECG numeric parameters (intervals) and interpretation (normal, abnormal not clinically significant, and abnormal clinically significant) at screening will be summarized using descriptive statistics.

5.10. Trial Protocol Deviations

Data from participants with any important protocol deviations during the trial will be summarized overall and for each category using descriptive statistics.

5.11. Intercurrent Events

The incidence of the intercurrent events for which the composite strategy is used in the primary analysis (see Section 1.2 for primary estimand and Sections 4.5 and 4.6 for classification rules) will be summarized using descriptive statistics. The summary will be presented for the mITT analysis set.

6. EFFICACY ANALYSIS

6.1. General

The mITT analysis set will be used for all efficacy analyses. Summaries will be presented by treatment group and indication (UC or CD).

Descriptive statistics for all efficacy endpoints will be summarized for the mITT analysis set. In addition, descriptive statistics will be provided for the ITT analysis set, which includes participants in the 1800 mg treatment group that were randomized to the trial prior to PA03 Rev01.

6.1.1. Efficacy Endpoints of Response and Remission at Week 14

The efficacy endpoints of response and remission at week 14 are presented for UC and CD in [Table 4](#) and [Table 5](#).

Table 4: Response and Remission Endpoints at Week 14 – UC

Endpoint	Definition	Classification
Clinical remission (MMS)	MMS of ≤ 2 points defined by: a stool frequency subscore of 0 or 1, rectal bleeding subscore of 0, an endoscopic subscore of 0 or 1, where a score of 1 does not include “friability”	Primary
Clinical remission 2 (MMS)	MMS of ≤ 2 points defined by: a stool frequency subscore of 0 or 1 and not greater than the baseline, rectal bleeding subscore of 0, an endoscopic subscore of 0 or 1, where a score of 1 does not include “friability”	Supplementary to primary
Clinical response (MMS)	≥ 2 points decrease in MSS AND at least a 30% reduction from baseline with either a decrease in rectal bleeding subscore of at least 1 or an absolute rectal bleeding subscore of less than or equal to 1	Secondary
Endoscopic improvement (Mayo endoscopic subscore)	Mayo endoscopic subscore of 0 or 1, where a score of 1 does not include “friability”	Secondary
Endoscopic remission (Mayo endoscopic subscore)	Mayo endoscopic sub-score of 0	Secondary
Clinical response (PRO2)	$\geq 50\%$ decrease in PRO2 from baseline	Secondary

Table 4: Response and Remission Endpoints at Week 14 – UC (Continued)

Endpoint	Definition	Classification
Clinical remission (PRO2)	rectal bleeding=0, and stool frequency=0	Secondary
Histological remission (RHI)	RHI ≤ 5	Exploratory
Histological remission (Geboes Index)	Geboes index score ≤ 3.1	Exploratory
Histologic-Endoscopic Mucosal Improvement (HEMI)	Mayo endoscopic subscore of 0 or 1 (where a score of 1 does not include “friability”) and Geboes score ≤ 3.1	Exploratory

Table 5: Response and Remission Endpoints at Week 14 – CD

Endpoint	Definition	Classification
Endoscopic response (SES-CD)	$\geq 50\%$ decrease in SES-CD from baseline	Primary
Endoscopic response 2 (SES-CD)	$> 50\%$ decrease in SES-CD from baseline, or a decrease of at least 2 points for subjects with a baseline score of 4 and isolated ileal disease	Supplementary to primary
Endoscopic response (MM-SES-CD)	$\geq 50\%$ decrease in MM-SES-CD from baseline	Secondary
Clinical response (CDAI)	≥ 100 -point decrease in CDAI score from baseline	Secondary
Clinical remission (CDAI)	CDAI score < 150	Secondary
Clinical response (PRO2)	$\geq 50\%$ decrease in PRO2 from baseline	Secondary
Clinical response 2 (PRO2)	$\geq 30\%$ decrease in PRO2 from baseline	Exploratory
Clinical remission (PRO2)	abdominal pain ≤ 1 , and stool frequency ≤ 3	Secondary
Clinical remission 2 (PRO2)	abdominal pain ≤ 1 , and stool frequency ≤ 1.5	Exploratory
Clinical remission 3 (PRO2)	abdominal pain ≤ 1 , and stool frequency ≤ 2.8	Exploratory
Endoscopic remission (SES-CD)	SES-CD score of 0-2	Exploratory
Endoscopic remission 2 (SES-CD)	SES-CD score of 0-4 with no individual subscore > 1	Exploratory
Histologic response (GHA)	$\geq 50\%$ decrease in GHA Score from baseline	Exploratory

Similar secondary/exploratory response and remission endpoints based on PRO2 and CDAI are defined at all timepoints where they are assessed. Details regarding the CDAI and PRO2-CD scores are provided in [Appendix 4](#) and [Appendix 5](#).

6.2. Primary Efficacy Endpoints and Analysis

6.2.1. Primary Endpoint

The primary endpoint is response (yes or no) at week 14, where response in UC participants is defined as clinical remission (based on MMS) and response in CD participants is defined as endoscopic response (based on SES-CD).

6.2.1.1. Primary Endpoint in Ulcerative Colitis – Clinical Remission

The primary efficacy endpoint in UC participants is clinical remission at week 14 based on the modified Mayo score (MMS), defined as follows: $MMS \leq 2$ with

- stool frequency subscore of 0 or 1, and
- rectal bleeding subscore of 0, and
- endoscopic subscore of 0 or 1, where a score of 1 does not include “friability”

Details regarding the endoscopy and the MMS are provided in Section 6 of the trial protocol.

6.2.1.2. Primary Endpoint in Crohn’s Disease – Endoscopic Response

The primary efficacy endpoint in CD participants is endoscopic response at week 14, defined as a reduction from baseline in Simple Endoscopic Score for Crohn’s Disease (SES-CD) of at least 50%.

6.2.2. Primary Efficacy Analysis

A Beta-binomial model with a non-informative Beta (1,1) prior will be used to analyze the primary response endpoint, clinical remission (for UC) or endoscopic response (for CD), hereafter denoted as “response”. The model will be fit separately for each dose within each indication.

Inference will be based on posterior distribution of the response rates. A TEV-48574 dose will be declared successful at the final analysis if the posterior probability that the response rate in the TEV-48574 dose is higher than the response rate in the placebo arm is ≥ 0.90 . Put another way, the success criterion for each dose within indication can be written as:

Posterior Probability (TEV-48574 response rate – placebo response rate >0) ≥ 0.90

The posterior distribution of (TEV-48574 response rate – placebo response rate) for each treatment group will be presented graphically. In addition, the following quantities will be presented:

- Posterior means of the response rates for TEV-48574 900 mg Q2W, TEV-48574 450 mg Q2W and placebo
- Two-sided 95% credible intervals for difference in response rates (TEV-48574 doses – placebo)

- For each TEV-48574 dose, Posterior Probability (TEV-48574 response rate – placebo response rate > 0)

[Appendix 1](#) provides details on the Beta-binomial model.

6.2.3. Sensitivity and Supplementary Analysis

The following sensitivity and supplementary analyses of the primary endpoint will be performed:

1. Tipping point analysis will be performed to test the robustness of the primary analysis conclusion to the non-response imputation of participants that discontinue the trial or have missing week 14 MMS (UC participant) or SES-CD (CD participants) data used in the primary analysis. The tipping point analysis will be conducted by varying the number of participants imputed as non-responders in the active and placebo groups.
2. A supplementary analysis for the primary endpoint using the response variables defined in the first supplementary estimand, clinical remission 2 (MMS) for UC and endoscopic response2 (SES-CD) for CD (see [Table 5](#)), will be performed. The primary analysis model will be used in this analysis.
3. A supplementary analysis for the primary efficacy variable will be performed using a logistic regression model fit separately to each indication with the following fixed effects: dose (as categorical variable), actual previous exposure to advanced IBD therapy (yes/no), and baseline MMS (UC participants) or SES-CD (CD participants).
 - Each comparison of TEV-48574 dose versus placebo will be tested (one-sided-) at a nominal significance level of $\alpha=0.1$.
 - Odds ratios (for each of the TEV-48574 doses versus placebo), associated two-sided 95% confidence intervals (CIs), and nominal one-sided- p-values will be reported.
4. Cochran-Mantel-Haenszel (CMH) test for pairwise comparisons between the active dose groups and placebo separately for UC and CD. Odds ratios (for each of the TEV-48574 doses versus placebo), difference in response rate, and the associated two-sided 95% CIs and nominal one-sided- p-values will be reported.
5. Cochran-Mantel-Haenszel (CMH) test for pairwise comparisons between the active dose groups and placebo separately for UC and CD, stratified by actual previous exposure to advanced IBD therapy (yes/no). The model will be used if data permits. Odds ratios (for each of the TEV-48574 doses versus placebo), difference in response rates, and the associated two-sided 95% CIs and nominal one-sided- p-values will be reported.
6. Bayesian logistic regression model for both UC and CD using a non-informative prior with a logistic regression model fit separately to each indication with the following fixed effects: dose (as categorical variable) and actual previous exposure to advanced IBD therapy (yes/no). The model will utilize a Jeffrey's prior which is a beta (1/2, 1/2).

6.2.4. Subgroup Analysis

The primary endpoints (UC and CD) will be evaluated using a Beta-binomial model with a non-informative Beta (1,1) prior as described in Section 6.2.2 for the subgroups below. The two-sided 95% credible intervals will be provided. A forest plot of the 95% two-sided credible intervals will be presented.

The primary endpoints (UC and CD) will also be evaluated for the subgroups using a logistic regression model as described in Section 6.2.3. Odds ratios (for each of the TEV-48574 doses versus placebo) and associated two-sided 95% CIs will be reported. A forest plot of the two-sided 95% CIs will be presented.

If there are <20 participants per subgroup within each indication, only descriptive statistics will be provided.

- Previous use of advanced IBD therapies (yes/no)
- Region (North America/Eastern EU - Poland/Eastern EU – Other/Western EU/Japan/Israel)
- Sex (female/male)
- BMI category (18.5<; \geq 18.5 to <25; \geq 25 to <30; \geq 30)
- Weight (<median, \geq median)
- Age category (18-40; 41-64; >65)
- Smoking status (current or former smoker: yes/no)
- Use of corticosteroids at baseline (yes/no)

Note: the median weight will be calculated for each indication separately.

For the subgroup analysis by previous use of advanced IBD therapies (yes/no), the posterior distributions of (TEV-48574 response rate – placebo response rate) in each stratum will be presented graphically for each treatment group. The logistic regression model will not include previous use of advanced IBD therapies (yes/no) as a covariate.

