2.2. Randomization and Blinding

This is a randomized, double-blind, placebo-controlled trial. Participants who meet all the inclusion criteria and none of the exclusion criteria will be randomly assigned to the 3 treatment arms: TEV-48574 900mg Q2W, TEV-48574 450mg Q2W or placebo in a 1:1:1 ratio, stratified by indication (UC or CD) and previous exposure to advanced therapy for IBD (yes/no) (biologics, JAK inhibitors, and S1P receptor modulators).

Table 1: Treatment Arms

Treatment Arm	Treatment (Q2W)
TEV-48574 900mg Q2W	TEV-48574 2250 mg (single loading dose)/900 mg (6 induction doses)
TEV-48574 450mg Q2W	TEV-48574 2250 mg (single loading dose)/450 mg (6 induction doses)
Placebo	Placebo

Q2W=every 2 weeks

Participants randomized prior to Amendment 03 with Revision 01 were randomized in a 1:1:1:1 ratio to TEV-48574 1800mg Q2W, TEV-48574 900mg Q2W, TEV-48574 450mg Q2W or placebo.

Participants will be randomly assigned to the treatment groups by means of a computer-generated randomization list using interactive-response technology.

Personnel who may be aware of IMP assignments will not be involved in the conduct of any trial procedures or assessment of any adverse events.

The participants, site, and sponsor trial team will be blinded until all participants complete the trial, and the database is locked for final analysis.

Pharmacokinetic, pharmacodynamics and immunogenicity samples will be collected for bioanalysis during the trial. Individuals responsible for sample bioanalysis and other responsible personnel may know who received test IMP and who received placebo IMP during the trial. Personnel responsible for bioanalysis will be provided with the randomization code to facilitate the analysis. However, the personnel responsible for bioanalysis will not have access to clinical safety and efficacy data and will provide concentration data to other personnel in a manner that will not identify individual participants (i.e., a dummy participant identifier will be linked to the concentration data of an individual participant).

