2.5. Sample Size and Power Considerations

A total trial sample size of approximately 240 participants is planned, with 120 participants (40 participants per dose arm) each for the 2 indications of UC and CD.

The sample size does not include participants that were randomized to the 1800 mg Q2W treatment group prior to Protocol Amendment 03 with Revision 01.

Assumptions:

The clinical remission and endoscopic response rates assumed in the sample size and related operating characteristics computations are as follows:

- Clinical remission rates in UC group: 8% for placebo; 30% for TEV-48574 groups, respectively
- Endoscopic response rates in CD group: 12% for placebo; 34% for TEV-48574 groups, respectively

Additional scenarios for remission (UC), response rates (CD) are assumed as outlined in [Table 2](#) to investigate the operating characteristics.

Table 2: Remission (UC), Response (CD) Rates Scenarios for Clinical Trial Simulations

Scenario	Indication	Placebo (%)	TEV-48574 450 mg Q2W (%)	TEV-48574 900 mg Q2W (%)
Null	UC	8	8	8
	CD	12	12	12

Table 2: Remission (UC), Response (CD) Rates Scenarios for Clinical Trial Simulations (Continued)

Scenario	Indication	Placebo (%)	TEV-48574 450 mg Q2W (%)	TEV-48574 900 mg Q2W (%)
Intermediate Efficacy	UC	8	20	20
	CD	12	25	25
Efficacy	UC	8	30	30
	CD	12	34	34
Efficacy-high dose only	UC	8	8	30
	CD	12	12	34

CD=Crohn's disease; Q2W=every 2 weeks; UC=ulcerative colitis.

Operating Characteristics:

Simulation-based operating characteristics for the analysis of the primary efficacy variable using a Bayesian Beta Binomial model are presented in [Table 3](#). This model uses a posterior probability cutoff of ≥ 0.90 to declare success at the final analysis.

Table 3: Operating Characteristics of Final Analysis

	UC			CD		
	TEV-48574 450 mg Q2W	TEV-48574 900 mg Q2W	At least 1 dose	TEV-48574 450 mg Q2W	TEV-48574 900 mg Q2W	At least 1 dose
Null	7.9%	7.9%	13.5%	9.6%	9.6%	16.1%
Intermediate efficacy	61.1%	61.1%	77.3%	59.3%	59.3%	75.9%
Efficacy	91.0%	91.0%	97.6%	87.1%	87.3%	95.5%
Efficacy-high dose only	7.9%	91.1%	91.1%	9.6%	87.2%	87.3%

CD=Crohn's disease; Q2W=every 2 weeks; UC=ulcerative colitis.

Beta-Binomial model with non-informative prior Beta(1,1); decision rule for declaring difference from placebo is based on having a posterior probability of ≥ 0.90 .

Note: Operating characteristics based on 500,000 simulations.

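### Section 6.2.4 reports treatment effects within each subgroup but never estimates how far the effect differs between subgroups

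*SAP*

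**What the plan says.** SAP section 6.2.4 names eight factors: previous advanced therapy, region, sex, BMI, weight (split at the median), age, smoking and baseline corticosteroid use. The primary endpoint is to be analysed with a "Beta-binomial model with a non-informative Beta (1,1) prior as described in Section 6.2.2 for the subgroups below", giving 95% credible intervals. The display is described as follows: "A forest plot of the 95% two-sided credible intervals will be presented". A second forest plot shows odds ratios of each dose against placebo from the logistic model.

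That logistic model (section 6.2.3, item 3) contains dose, previous advanced therapy and the baseline score as main effects. For previous advanced therapy, which is also a randomization stratum (section 2.2), the posterior distributions of the rate difference "in each stratum will be presented graphically for each treatment group". A subgroup with fewer than 20 participants within an indication gets descriptive statistics only.

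The SAP contains no dose-by-subgroup term, ratio of odds ratios, difference between subgroup differences or other measure of heterogeneity. It gives no guidance on how the plots should be read.

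**The concern.** A subgroup analysis asks whether the treatment effect differs between the levels of a factor. The planned output gives the effect at each level and leaves the comparison to the eye. With about 20 participants per arm per level, each interval is wide enough to cross zero by chance. One level may therefore appear to show an effect and the other not, although the true effects are the same.

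This matters most for previous advanced therapy. A mistaken impression that the drug works only in one of these two strata could influence the population chosen for the next trial.

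**Working it through.** **Inputs.**
- Size: "120 participants (40 participants per dose arm) each for the 2 indications of UC and CD" (section 2.5).
- Allocation: "TEV-48574 900mg Q2W, TEV-48574 450mg Q2W or placebo in a 1:1:1 ratio" (section 2.2).
- Full planned effect: "Clinical remission rates in UC group: 8% for placebo; 30% for TEV-48574 groups, respectively" and "Endoscopic response rates in CD group: 12% for placebo; 34% for TEV-48574 groups, respectively" (section 2.5), a difference of 22 points in each indication.
- Intermediate scenario (Table 2): 8% vs 20% (UC), 12% vs 25% (CD). Null: 8% and 12% in all arms.
- Split: 20 per arm per level. This follows from the median split for weight, apart from chance imbalance between arms. For every other factor it is an assumption, so uneven splits were also tried.

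**Step 1: reproduce the plan's own figures.** On its decision rule, section 2.5 says "This model uses a posterior probability cutoff of" at least 0.90. All outcomes of 40 vs 40 were enumerated, with P(active rate > placebo rate) computed from Beta(1+x, 1+n−x) posteriors. For a single dose:

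| Scenario | UC, Table 3 | UC, recomputed | CD, Table 3 | CD, recomputed |
|---|---|---|---|---|
| Null | 7.9% | 7.9% | 9.6% | 9.6% |
| Intermediate | 61.1% | 61.0% | 59.3% | 59.3% |
| Efficacy | 91.0% | 91.0% | 87.1–87.3% | 87.2% |

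The model is therefore implemented as the SAP intends.

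**Step 2: identical effects in two halves.** Let a be the probability that the 95% credible interval in one half (20 vs 20) excludes zero, that is, a posterior probability of at least 0.975 or at most 0.025. The halves contain different participants, so the probability that exactly one excludes zero is 2a(1−a).

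| Scenario | a, UC | 2a(1−a), UC | a, CD | 2a(1−a), CD |
|---|---|---|---|---|
| Efficacy | 0.439 | 2 × 0.439 × 0.561 = 49% | 0.379 | 2 × 0.379 × 0.621 = 47% |
| Intermediate | 0.187 | 2 × 0.187 × 0.813 = 30% | 0.180 | 2 × 0.180 × 0.820 = 30% |
| Null | 0.029 | 2 × 0.029 × 0.971 = 6% | 0.045 | 2 × 0.045 × 0.955 = 9% |

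Splits of 24:16 to 30:10 per arm give 50–56% (UC) and 47–52% (CD) at the full planned effect. All figures are for one dose and one two-level factor.

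**Step 3: the direct contrast.** Let δ = (active − placebo in half A) − (active − placebo in half B), drawn from the four independent Beta posteriors. In 6,000 simulated trials with identical effects at the full planned size and a 20:20 split, the 95% interval for δ excluded zero in 3.6% (UC) and 3.7% (CD). Its mean half-width was 32 points (UC) and 34 points (CD).

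**Step 4: what the contrast can detect.** If the drug worked in one half only (UC: 30% vs 8% in one, 8% vs 8% in the other; CD likewise with 34% and 12%), the interval for δ would exclude zero in about 24% (UC) and 22% (CD) of trials.

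**Step 5: empty cells on the odds-ratio scale.** The chance that at least one placebo half has no responder is 1 − (1 − 0.92²⁰)² = 34% (UC) and 1 − (1 − 0.88²⁰)² = 15% (CD). The maximum-likelihood ratio of odds ratios is then not finite.

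**The case against.** The strongest reply is that section 6.2.4 sets no subgroup success rule, p-value or claim. A reader might infer that the SAP will declare a subgroup difference when one interval excludes zero and the other does not, or that the 0.90 cutoff of section 6.2.2 is to be applied stratum by stratum. Neither is written there; the section takes the model from 6.2.2 and asks for intervals and plots. A forest plot also shows overlap: with identical effects, the two intervals overlap in more than 99% of simulated trials. This stands, and it rules out saying that the plan makes identical effects look different in half of all trials.

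Two further points stand in part. For previous advanced therapy the plan shows full posterior curves, which discourage a yes/no reading, but there is still no contrast. A reader could also approximate the contrast from the planned output: the difference of the interval centres, with half-width √(w_A² + w_B²), comes within about 0.4 points of the direct half-width on average. So the information is not lost; it is left for each reader to reconstruct.

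Lastly, the contrast seldom settles the question (step 4), and section 7 makes no multiplicity adjustment. That limits what the contrast can claim. It is no reason to omit it, since its width shows how little these subgroups can establish.

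**Conclusion.** The omission is real and its consequence is minor. The SAP specifies its subgroup analysis in detail but leaves out an estimate of how far the effect differs between subgroups.

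The discordance of 49% (UC) and 47% (CD) rests on the full planned effect, identical true effects, one dose, one two-level factor, an even split (assumed except for median weight) and a reader who contrasts exclusion of zero with inclusion. It falls to about 30% in the intermediate scenario and to 6–9% under the null. The direct contrast flags a difference in about 4% of trials at the full planned effect.

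No decision in the SAP depends on the subgroup results, and primary inference is unaffected. This is a cheap reporting improvement.

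**What to change.** In section 6.2.4, for previous advanced therapy and the other two-level factors (sex, median weight, smoking, baseline corticosteroids) whose levels both meet the 20-participant rule, add to the Beta-binomial forest plot, for each dose, the posterior mean and 95% credible interval of the difference between the two subgroup effects. It comes from the Beta posteriors already fitted. No test or threshold is needed.

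Label it exploratory and unadjusted, and state that an interval including zero does not show that the effects are equal, citing the half-width and detection figures above.

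A dose-by-subgroup term in the logistic model is optional; if used, it needs a penalised or exact fallback for empty cells. Contrasts of each level against the rest for region, BMI and age are not needed: they would require pooled posteriors that are not planned and would sit awkwardly with the 20-participant rule.

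The cost is a few lines of SAP text and one column in the plot. The downside is up to 5 factors × 2 doses × 2 indications = 20 imprecise, unadjusted contrasts. At 3–4% each, 0.6 to 0.8 of them would be expected to exclude zero by chance if effects were identical throughout.

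### The subgroup logistic models in SAP 6.2.4 have no fallback for separation, and in the smallest subgroups admitted the dose odds ratios would often not be finite

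*SAP*

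**What the plan says.** SAP Section 6.2.4 plans two analyses of the primary endpoint in each subgroup. The first is the Beta-binomial model with a Beta(1,1) prior. The second is logistic regression: "The primary endpoints (UC and CD) will also be evaluated for the subgroups using a logistic regression model as described in Section 6.2.3". That model has fixed effects for "dose (as categorical variable), actual previous exposure to advanced IBD therapy (yes/no), and baseline MMS (UC participants) or SES-CD (CD participants"). With three dose levels this is five parameters including the intercept. In the subgroup analysis by prior advanced therapy it is four, because "The logistic regression model will not include previous use of advanced IBD therapies (yes/no) as a covariate".

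The output is fixed: "Odds ratios (for each of the TEV-48574 doses versus placebo) and associated two-sided 95% CIs will be reported", with a forest plot. The only size restriction applies when there are fewer than 20 "participants per subgroup within each indication, only descriptive statistics will be provided". The sentence names no arm and sets no minimum number of responders. No penalised, exact or other fallback is given for the logistic model. A feasibility clause (use the model if the data permit) appears in Section 6.2.3, but only for the stratified CMH test.

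**The concern.** When an arm has no responders, ordinary maximum likelihood gives no finite log odds ratio for comparisons with that arm. If that arm is placebo, both dose odds ratios are lost at once, because placebo is the reference for each. Low placebo rates and small subgroups make this a realistic event.

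Two things are at stake in the odds-ratio forest plot. Some rows would be blank or would show very large estimates with unusable intervals, and the SAP does not say how to display them. The rows that do show a finite estimate would also have been selected on outcome, since they are the subgroups in which a placebo participant happened to respond. A rule chosen after unblinding to deal with this would be data-driven.

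**Working it through.** **Inputs from the SAP.**
- Allocation (Section 2.2): "TEV-48574 900mg Q2W, TEV-48574 450mg Q2W or placebo in a 1:1:1 ratio".
- Sample size (Section 2.5): "with 120 participants (40 participants per dose arm) each for the 2 indications of UC and CD".
- Planning rates (Section 2.5): UC 8% placebo and 30% active; CD 12% placebo and 34% active.
- Subgroup threshold of 20 (Section 6.2.4) and the model (Section 6.2.3), as above.

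**Step 1: reproduce the plan's own figures.** The SAP gives no operating characteristics for the subgroup models. Table 3 can be used to check the rates and arm sizes. Exact enumeration at 40 per arm, with Beta(1,1) priors and a 0.90 cutoff, gives for each dose / at least one dose:

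| Scenario | Recomputed | SAP Table 3 |
|---|---|---|
| UC null | 7.9% / 13.5% | 7.9% / 13.5% |
| UC efficacy | 91.0% / 97.6% | 91.0% / 97.6% |
| CD null | 9.6% / 16.1% | 9.6% / 16.1% |
| CD efficacy | 87.2% / 95.5% | 87.1–87.3% / 95.5% |

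The inputs are therefore read correctly.

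**Step 2: smallest admitted subgroup.** Twenty participants split 1:1:1 as about 7, 7 and 6. With 6 on placebo, the expected number of responders is 6 × 0.08 + 14 × 0.30 = 4.7 in UC and 6 × 0.12 + 14 × 0.34 = 5.5 in CD, for a five-parameter model.

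**Step 3: chance of no placebo responder.** With n on placebo and response rate p, this is (1 − p)^n.

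| Placebo n | UC, 0.92^n | CD, 0.88^n |
|---|---|---|
| 7 | 56% | 41% |
| 10 | 43% | 28% |
| 20 | 19% | 8% |

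In that event the likelihood keeps increasing as the intercept goes to minus infinity and both dose coefficients go to plus infinity with their sums with the intercept held fixed. Neither odds ratio has a finite estimate. This step needs no assumption about the covariates.

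**Step 4: add the covariates.** Adjustment can create further separation. The planned model was simulated and linear programming was used to detect separation (1,500 replicates per setting at the efficacy rates). The SAP gives no covariate distributions, so it was assumed that half the participants had prior exposure, that the baseline score has a generic distribution, and that neither covariate is related to outcome. At 20–21 participants, separation occurs in roughly 63–67% of UC and 48–56% of CD subgroups. The upper part of the CD range reflects variation between runs and whether any separation is counted or only separation that affects a dose term. At least one dose odds ratio is not finite in 46% (UC) and 31% (CD) at 30 participants, 33% and 17% at 40, and 20% and 9% at 60. Moving the exposure proportion moderately either side of one half left the share with a non-finite dose odds ratio essentially unchanged.

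**Step 5: selection among the finite rows.** Given at least one responder among 7 on placebo, the expected observed placebo rate is 0.08 / (1 − 0.558) = 18% in UC and 0.12 / (1 − 0.409) = 20% in CD, against 8% and 12%. The odds ratios that can be shown therefore tend towards no effect.

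**Step 6: where subgroups might fall.** At 120 per indication, six region levels average 120 / 6 = 20, four BMI levels 120 / 4 = 30, three age levels 120 / 3 = 40, and a median split on weight gives about 120 / 2 = 60. These are averages only.

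**The case against.** **Scope.** Seven per arm is the boundary case. Five of the eight subgroup factors are binary, and the median weight split has about 20 per arm, where the problem is much smaller. A reader might infer from the region and BMI averages that many subgroups will sit near the threshold. The SAP does not support that: it gives no distribution over region or BMI, and uneven enrolment would put some levels below 20, where only descriptive statistics are planned, and others well above. This objection stands.

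**Wording of the model.** Section 6.2.3 says logistic regression without naming maximum likelihood. The ordinary fit is the natural reading, but it is an inference. That supports naming the estimation method.

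**Importance.** The Beta-binomial subgroup analysis always gives a proper interval and has its own forest plot. No decision rests on the subgroup odds ratios. This stands and sets the severity.

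**Tempting remedies.** A threshold of 20 per arm would need about 60 participants per subgroup. It would remove the smaller half of any unequal binary split and most region and BMI levels. Because the same sentence governs both analyses, it would also remove Beta-binomial intervals that work perfectly well. It would still leave about 20% (UC) and 9% (CD) with a non-finite dose odds ratio. Requiring at least one responder per arm would build in the selection shown in Step 5. Neither is recommended.

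**Conclusion.** The point holds as a gap in a supportive analysis. Section 6.2.4 commits to odds ratios and intervals from a logistic model in any subgroup of 20 or more across all arms and has no provision for separation. At about 7 per arm and the planning rates, the zero-placebo event alone has probability 56% (UC) and 41% (CD); with covariates, separation is roughly 63–67% and 48–56%. The zero-cell figures rest only on the SAP's planning rates and 1:1:1 allocation. The covariate-adjusted figures also rest on the assumptions in Step 4.

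A reader might go further and infer that the subgroup analysis as a whole cannot be estimated, or that the trial's conclusion is at risk. The documents do not support either. Even at the smallest size the CD model is estimable about half the time, the risk falls steadily as subgroups grow, the Beta-binomial intervals are untouched, and success is declared on the primary posterior probability alone (Section 6.2.2). Severity: minor.

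**What to change.** In Section 6.2.4, state that the subgroup logistic models are fitted by Firth penalised likelihood with profile-likelihood confidence intervals, and that the number of responders and participants in each arm is shown beside each odds ratio in the forest plot. Keep the 20-participant threshold and the Beta-binomial subgroup analysis as written, and add neither a per-arm threshold nor a minimum number of responders.

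The cost is a sentence or two in the SAP and a change of estimation option in the SAS program, made before unblinding. The statistical downside is that small-sample odds ratios are shrunk towards no effect and their intervals remain wide. The responder counts let the reader see when an estimate rests on an empty cell.
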